3.2 Rationale for study design, doses and control groups

This single-center, open-label, randomized, 2-way cross-over study is designed to assess the PD and PK interaction between clopidogrel and esomeprazole 20 mg/ASA 81 mg. The crossover design improves reliability with each healthy volunteer being his/her own control by eliminating the impact of between-subject variability in the clopidogrel response.

The study will be conducted in healthy male and female volunteers to avoid interference from disease processes or other drugs. The selection criteria are defined such that subjects selected for participation in the study are known to be free from any significant illness.

Pharmacokinetic and PD sampling in each treatment period is judged to be sufficient to fulfil the objectives of the study.

The combination product esomeprazole/ASA will be developed using 2 strengths of esomeprazole (20 mg and 40 mg) and the lower strength will be used in this study. Two strengths of ASA (81 mg and 325 mg) will also be developed. For safety reasons, only the lower strength of ASA, 81 mg, will be used in this study. The recommended maintenance dose of clopidogrel, 75 mg, will be administered.

Clopidogrel will be administered for 9 days in order to reach steady-state conditions (steady state is reached between Day 3 and Day 7 (Plavix® Prescribing Information). A 5 day co-administration of esomeprazole 20 mg/ASA 81 mg is chosen to ensure steady-state of esomeprazole and to ensure full potential inhibition.

Due to irreversible binding with AMC, platelets are affected for the remainder of their lifespan (approximately 7 to 10 days) and recovery of normal platelet function occurs at a rate consistent with platelet turnover. The washout period of 14 days will ensure complete platelet turnover between treatment periods.

4. SUBJECT SELECTION CRITERIA

Investigator(s) should keep a record, the subject screening log, of healthy volunteers who entered pre-study screening.

Each healthy volunteer should meet all of the inclusion criteria and none of the exclusion criteria for this study before randomization. Under no circumstances can there be exceptions to this rule.

4.1 Inclusion criteria

For inclusion in the study, healthy volunteers should fulfil the following criteria:

- 1. Provision of informed consent prior to any study specific procedures (including pharmacogenetic sampling for CYP2C19 genotyping)
- Male (aged between 18 and 45 years inclusive) or female (aged between 18 and 55 years inclusive) healthy volunteers with suitable veins for cannulation or repeated vein puncture. Female healthy volunteers must be of non-childbearing potential (post-menopausal, have had a hysterectomy and/or bilateral oophorectomy) or be of childbearing potential, be non-lactating and have a negative serum human chorionic gonadotropin (S-hCG) pregnancy test during the pre-entry visit and be using 1 clinically accepted method of contraception. Clinically accepted methods of contraception that may be used by the subject and/or partner include: diaphragm with spermicide, intrauterine device (IUD, except for Mirena®) or condom with vaginal spermicide. Females will be defined as postmenopausal if last menstruation period was >1 year ago and serum follicle stimulating hormone (FSH) is within the postmenopausal range, or if age >50 years and with last menstruation period >2 years ago.
- 3. Have a body mass index between 19 and 30 kg/m² inclusive
- 4. No clinically significant abnormal findings at the physical examination at the preentry visit, as judged by the investigator

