3.1 Overall study design and flow chart

The study will be performed at Quintiles AB, Uppsala, Sweden. This is an open-label, randomized, 2-way cross-over study designed to assess the PD and PK interaction between clopidogrel and esomeprazole 20 mg/ASA 81 mg. Fifty-nine (59) healthy male and female volunteers will be enrolled and randomized to treatment.

The total study duration for each healthy volunteer is approximately 2.5 months. This includes a pre-entry visit within 28 days prior to randomization, 2 treatment periods of 9 days, washout periods of at least 14 days between the treatment periods (ie, between the last dose in period 1 and the first dose in period 2) and a follow-up visit 7 to 10 days after the last dose. See Figure 1.

In each treatment period, the healthy volunteers will arrive at the study unit on Day -1 and start treatment on Day 1. For treatment A, the healthy volunteers will take the subsequent doses on Days 2 to 8 at home and receive the dose on Day 9 at the study unit (they will return to the study unit in the evening of Day 8). For treatment B, the healthy volunteers will take the subsequent doses on Days 2 to 4 at home and they will return to the study unit to receive the doses on Days 5 to 9.

Figure 1 Study flow chart

- a Healthy volunteers will be administered the following treatments in randomized order (see Section 5.5.2) in Period 1 and 2:
 - Treatment A: clopidogrel 75 mg once daily for 9 days
 - Treatment B: clopidogrel 75 mg once daily for 4 days followed by esomeprazole 20 mg/ASA 81 mg with clopidogrel 75 mg once daily for 5 days
- b Investigational product (IP, esomeprazole 20 mg/ASA 81 mg and clopidogrel)
- c The washout period will be at least 14 days between the last dose in period 1 and the first dose in period 2.

Healthy volunteers will be administered IP for 9 days. Blood sampling for PD assessment will be drawn on Day -1 (Period 1)/pre-dose on Day 1 (Period 2) as baseline and 24 h after dose on Day 9. Blood samples for determination of AMC will be drawn pre-dose and 0.25, 0.5, 1, 1.5, 2, 3, 4, 6, 8, 10 and 12 h after the last dose on Day 9. Safety monitoring will be performed during the treatment periods. Standardized food will be served during the residential periods. The study plan and study time schedule are found in Table 1 and Table 2, respectively.

A genetic sample will be taken to assess CYP2C19 status on Day -1 in Period 1, once the informed consent has been signed.

Table 1 Study plan

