Event	Pre-entry	Perio	d 1	Period 2		Follow-up	
Study Day	within 28 days prior to randomization	Day -1 (admission)	Day 1 to 10 ^a	Day -1 (admission)	Day 1 to 10 ^a	7-10 days after the last dose	
Informed consent ^b	X						
Inclusion/exclusion criteria	X	X	X^{c}				
Randomization			X^{d}				
Demographics	X						
Body weight and height	X						
Nicotine, alcohol and caffeine use	X						
Medical and surgical history	X						
Physical examination	X					X	
Laboratory screening ^e	X	X	X^{f}	X	X^{f}	X	
Alcohol and drug screen	X	X		X			
CYP2C19 blood sample		X					
Paper ECG (pECG)	X	X		X		X	
Vital signs (BP/pulse)	X	X	X^{g}	X	X^g	X	
Administration of IP			X^h		X^h		
PK blood sampling			X^{i}		X^{i}		
PD blood sampling		X	X^{j}		X^k		
Standardized food ¹		X	X	X	X		
Concomitant medication	X	X	X	X	X	X	
AE/serious adverse event (SAE) recording ^m	X	X	X	X	X	X	

- a For treatment A, the subjects will leave the study unit after dosing on Day 1 and return in the evening on Day 8. For treatment B, the subjects will leave the study unit after dosing on Day 1 and return prior to dose on Day 5. For both treatment periods, they will be discharged from the study unit after the assessments 24 h post dose on Day 9 (ie, on Day 10).
- b If an extra pre-entry visit is needed prior to randomization, the healthy volunteers will only need to sign the informed consent once.
- c Only AEs and concomitant medication will be checked before randomization on Day 1.
- d Randomization will be done on Day 1.
- e See Section 6.3.5 for assessments. At the pre-entry visit, also including human immunodeficiency virus (HIV), hepatitis B and C.
- f On Day 9 (see Table 2)
- g Pre-dose on Days 1 and 9 (see Table 2)
- h For treatment A, administration will take place at study unit on Day 1, at home on Days 2 to 8 and at the study unit on Day 9. For treatment B, administration will take place at study unit on Day 1, at home on Days 2 to 4 and at the study unit on Days 5 to 9.
- i Pre-dose and 0.25, 0.5, 1, 1.5, 2, 3, 4, 6, 8, 10 and 12 h after the last dose on Day 9 (see Table 2)
- j 24 h post dose on Day 9 (see Table 2). The baseline sample will be obtained on Day -1.
- k Pre-dose on Day 1 (as baseline) and at 24 h post dose on Day 9 (see Table 2)
- 1 Standardized food will be served during the residential periods.
- m Serious adverse events will be collected from the time when informed consent is obtained until the follow up visit.

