6.2 Data collection and enrolment

Each healthy volunteer will undergo an enrolment medical examination within 28 days before first dose of IP, see also Table 1. This will consist of:

- Demographic data: date of birth, sex and race
- Weight (measured in kg), height (measured in cm, without shoes) and habits of nicotine, alcohol and caffeine consumption
- Significant medical and surgical history
- A physical examination including general appearance, skin, head and neck, lymph nodes, thyroid, musculoskeletal/extremities, cardiovascular system, respiratory system, abdomen and a neurological examination (only reflexes)
- Resting pulse and BP measurement
- Blood sample for clinical chemistry, haematology and coagulation (including S-hCG for females), a mid-stream urine sample for urinalysis and drugs of abuse test, a faeces sample for F-Hb and an alcohol breath test
- A blood sample to test for hepatitis B surface antigen and antibodies to hepatitis C virus and HIV, for the safety of the site personnel
- pECG
- Check of concomitant medications and SAEs

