6.3.5 Laboratory safety assessment

Blood, urine and faeces samples for determination of clinical chemistry, haematology, coagulation, urinalysis and F-Hb will be taken at the times indicated in the study plan (see Table 1).

The following laboratory variables will be measured:

Table 3 Laboratory variables

Clinical chemistry	Haematology		
S-Alanine Aminotransferase	B-Hb		
S-Aspartate Aminotransferase	B-Leukocyte count		
S-Alkaline Phosphatase	B-Platelet count		
S-Bilirubin, total			
S-Calcium, total	Coagulation		
S-Creatinine	P-Prothrombin complex (International normalized ratio) ^a		
S-C-reactive protein (high sensitive)	P-APTT ^a		
S-Potassium			
S-Sodium	Urinalysis		
S-hCG (females) ^{a, b}	U-Hb (dipstick)		
S-FSH ^c	U-Protein (dipstick)		
	U-Glucose (dipstick)		
Faeces			
F-Hb ^a			

- a Only at the pre-entry visit
- b Females only
- c Only at the pre-entry visit and only for all postmenopausal women, except for women >50 years old who had their last menstruation >2 years ago.

At the pre-entry visit all healthy volunteers will be tested for HIV, hepatitis B surface antigen and antibodies to hepatitis C. Alcohol breath test will be performed and urine will be tested for drugs of abuse (amphetamines, opiates, benzodiazepine, cannabinoid, cocaine) at the pre-entry visit and on Day -1 in all treatment periods.

The safety laboratory samples will be analyzed by Quintiles AB, Safety Laboratory, Uppsala, Sweden using standard methods.

Laboratory values outside the reference limits suspected to be of any clinical significance will be retaken. Healthy volunteers in whom the suspected clinical significance is confirmed on repeated sampling will either not be included or, if already included, will be followed until normalization or for as long as medically indicated.

For reporting of AEs based on examinations and tests, see Section 6.3.3. For blood volume, see Section 7.1.

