13.3 Pregnancy

All outcomes of pregnancy should be reported to AstraZeneca.

Females of childbearing potential must adhere to the birth control methods outlined in Section 4.1. If the Investigator receives information that a pregnancy has occurred during the study despite these restrictions, the designated Quintiles representative should be informed.

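### Pregnancy is tested only at the pre-entry visit, so the result can be 28 days old at the first Period 1 dose and at least 50 days old at the first Period 2 dose, with no scheduled recheck before either period

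*Protocol*

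**What the plan says.** Protocol 4.1, criterion 2, admits women of childbearing potential who use one accepted contraceptive method, are not lactating, and "have a negative serum human chorionic gonadotropin (S-hCG) pregnancy test during the pre-entry visit". Section 5.1 repeats the contraception requirement for the conduct of the study.

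In Table 3 (section 6.3.5), S-hCG carries a footnote that reads "Only at the pre-entry visit". The laboratory ticks in Table 1 on Day -1 and Day 9 of each period and at follow-up therefore do not include it.

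Section 3.1 places the pre-entry visit "within 28 days prior to randomization".

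Table 1 ticks the inclusion/exclusion check at pre-entry and, in Period 1, on Day -1 and Day 1. The Day 1 check is restricted to adverse events and concomitant medication. No eligibility check is ticked in Period 2.

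Section 13.3 wants every pregnancy outcome reported to the sponsor. Its procedure for a pregnancy arising during the study opens with "If the Investigator receives information that a pregnancy has occurred during the study despite these restrictions".

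**The concern.** Pregnancy status can change within the interval the plan allows between the test and dosing, and the plan then adds a second treatment period at least 22 days after the first one starts. A woman who conceives after screening and does not know it would go through both admissions without any scheduled procedure showing it.

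What is at stake is the safety of healthy volunteers, who by section 1.3 gain no direct medical benefit. They receive clopidogrel in both periods and the esomeprazole/ASA capsule for five days of Treatment B. A second, smaller matter is reporting: with no test at follow-up, the duty in 13.3 depends on volunteers recognising a pregnancy and telling the site.

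The plan also re-measures other conditions that can change. Alcohol and drug screens, the ECG and the clinical chemistry and haematology panel are all repeated on Day -1 of both periods.

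**Working it through.** The plan states no figure for the age of the test, so there is none to reproduce. The check is calendar arithmetic from the protocol's own windows, followed by a search for any other step that would detect a pregnancy.

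**Inputs**

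- Screening limit: 28 days. Section 3.1 counts it from randomization. Section 6.2 counts it from the first dose: "Each healthy volunteer will undergo an enrolment medical examination within 28 days before first dose of IP". The two coincide, because Table 1 states "Randomization will be done on Day 1", which is also the first dosing day.
- Day 1 to Day 9 of a period: 8 days elapsed.
- Washout: at least 14 days from the last Period 1 dose to the first Period 2 dose (section 3.1).
- Follow-up: 7 to 10 days after the last dose.

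**Formula.** Let *s* be the number of days from the pre-entry test to Period 1 Day 1. The age of the test is then:

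- Period 1 Day 1: *s*
- Period 1 Day 9: *s* + 8
- Period 2 Day 1: at least *s* + 8 + 14 = *s* + 22
- Period 2 Day 9: at least *s* + 22 + 8 = *s* + 30

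| Test taken (days before Period 1 Day 1) | Period 1 Day 1 | Period 1 Day 9 | Period 2 Day 1 | Period 2 Day 9 |
|---|---|---|---|---|
| 28 | 28 | 36 | at least 50 | at least 58 |
| 14 | 14 | 22 | at least 36 | at least 44 |
| 7 | 7 | 15 | at least 29 | at least 37 |
| 1 | 1 | 9 | at least 23 | at least 31 |

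**Plausibility.** At the screening limit with the minimum washout, follow-up falls at 58 + 7 = 65 to 58 + 10 = 68 days. The stated total of about 2.5 months is roughly 76 days. The schedule is therefore compatible with the plan and leaves about 8 to 11 days for a longer washout, although no maximum is set.

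**Would any other scheduled step detect a pregnancy?**

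- Period 1 Day -1: eligibility is checked, but the only S-hCG result available is the pre-entry one.
- Period 1 Day 1: adverse events and concomitant medication only.
- Period 2 Day -1: alcohol and drug screen, ECG, vital signs and safety laboratory tests without S-hCG.
- Day 9 of each period and follow-up: safety laboratory tests without S-hCG.
- An optional extra pre-entry visit (Table 1): it could repeat the test, but only before randomization and not by rule.

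None of these would do so.

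**Is serum available?** Table 1 has six laboratory occasions: pre-entry, Day -1 and Day 9 in each of two periods, and follow-up. Table 4 lists six clinical chemistry samples, one for each. It lists no separate S-hCG tube, and section 6.2 includes S-hCG in the pre-entry safety blood sample.

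**The case against.** The strongest reply is that nothing here is inconsistent. Criterion 2, Table 3 and Table 1 all specify one S-hCG at pre-entry, and section 4 applies the criteria before randomization. A reader might infer that dosing a woman who conceived later would breach the inclusion criterion. It would not: the criterion asks for a negative result at the pre-entry visit and is formally met. What stays unverified is that she is not pregnant when dosed. This part of the reply stands.

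Safeguards also exist. Contraception is required throughout. Section 5.3 calls for a discussion between the sponsor's physician and the investigator if a volunteer later fails the study criteria. Section 5.8 lists unmet eligibility as a reason to discontinue, and section 6.3.3 has staff ask an open health question. These lower the probability of an affected volunteer or govern what follows once a pregnancy is known. None would reveal an unrecognised one.

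Single testing is not unique to pregnancy. The coagulation tests, faecal haemoglobin and the viral serology are also done only at pre-entry. So the contrast with the repeated tests shows that repetition is practicable; it does not show that S-hCG is a lone omission.

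Fifty days is the figure for a woman screened at the limit, not for everyone, and the age of a test is not a probability of pregnancy. Both points are right. The 23-day minimum shows, however, that late screening does not remove the Period 2 gap.

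Finally, a reader might assume that a Day -1 laboratory result already has to be back before dosing in both periods because of the platelet criterion. That criterion governs entry to the study, and Table 1 has no eligibility check in Period 2, so the assumption is supported for Period 1 only.

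**Conclusion.** The concern holds as a weakness in the safety schedule. It is neither an internal contradiction nor a breach of criterion 2. The protocol expressly restricts S-hCG to one test, so this is not a detail left to another document.

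For a woman screened at the 28-day limit, the result is 28 days old at the first Period 1 dose, at least 50 days old at the first Period 2 dose and at least 58 days old at the last dose. The Period 2 figures assume the minimum washout and are therefore lower bounds. With screening the day before Day 1, the result is still at least 23 days old at the start of Period 2.

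The number of women exposed to this gap cannot be given. The protocol fixes neither the split by sex among the 59 volunteers nor the proportion of childbearing potential, and it gives no figure from which a pregnancy rate could be derived. The sample size, the mIPA comparison and the pharmacokinetic analyses are unaffected. The case for change rests on a clear safety gap and a small cost.

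**What to change.** In Table 3, give S-hCG its own footnote. The present one also covers the coagulation and faecal tests, which need not change. The new footnote should state that, for women of childbearing potential, S-hCG is measured at pre-entry, on Day -1 of Period 1, on Day -1 of Period 2, and at follow-up. The follow-up test prevents no dosing; its purpose is to support the reporting required by 13.3. All three added tests can use the clinical chemistry serum already drawn at those visits.

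The protocol should also state how a positive result bears on dosing and continuation. That rule is for the sponsor and investigator to define, consistently with sections 5.3, 5.8 and 13.3; none is proposed here.

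Cost: up to three more assays per woman of childbearing potential, with no added visit or venepuncture, provided the existing chemistry sample suffices as it appears to at pre-entry. For the Period 2 test to inform dosing, its Day -1 result must be back before Day 1, which is a new turnaround requirement. In Period 1, the Day -1 platelet criterion already implies one.

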4.2 Exclusion criteria

Healthy volunteers should not enter the study if any of the following exclusion criteria are fulfilled:

- 1. Involvement in the planning and/or conduct of the study (applies to both AstraZeneca staff and staff at the study site)
- 2. Previous randomization in the present study
- 3. Participation in another clinical study with an IP during the last 3 months. The period of exclusion begins at the time of the last dose in the prior study. Note: healthy volunteers consented and screened but not dosed in this study or a previous phase I study, will not be excluded.
- 4. History of any clinically significant disease or disorder which, in the opinion of the investigator, may either put the healthy volunteer at risk because of participation in the study, or influence the results or the healthy volunteer's ability to participate in the study, eg, history of any bleeding disorder or ongoing or history of liver disease
- 5. History or presence of gastrointestinal (GI) (eg, GI ulcer), hepatic or renal disease or any other condition known to interfere with absorption, distribution, metabolism or excretion of drugs
- 6. Any clinically significant illness within 4 weeks of the first administration of IP. Any medical/surgical procedure or trauma within 3 months of the treatment period; scheduled surgery, including dental surgery, within 2 weeks of the scheduled completion of the study.
- 7. Any clinically significant abnormalities in clinical chemistry, haematology (eg, history or presence of thrombocytopenia, abnormal activated partial thromboplastin time (APTT) and prothrombin complex) or urinalysis (>+1 urine-haemoglobin (U-Hb) at the pre-entry visit) or positive feaces-haemoglobin (F-Hb) results, as judged by the investigator
- 8. Healthy volunteers who will need to drastically change their lifestyle activities in order to comply with restrictions during the study considering their exercise volume or their diet
- 9. Suspicion of or known Gilbert's disease
- 10. Any positive result on screening for hepatitis B surface antigen, hepatitis C antibody and HIV
- 11. After 10 min supine rest abnormal vital signs (diastolic blood pressure (BP), systolic BP, pulse rate) as judged by the investigator

- 12. Any clinically important abnormalities in rhythm, conduction or morphology of resting ECG. This includes healthy volunteers with any of the following:
 - Clinically significant PR (PQ) interval prolongation
 - Intermittent second or third degree AV block
 - Incomplete, full or intermittent bundle branch block (QRS <110 ms with normal QRS and T wave morphology is acceptable if there is no evidence of left ventricular hypertrophy)
 - Abnormal T wave morphology, particularly in the protocol defined primary lead
- 13. Prolonged QTcF >450 ms or shortened QTcF <350 ms or family history of long QT syndrome
- 14. Known or suspected history of drug abuse as judged by the investigator
- 15. Smoking or other sort of nicotine use within the previous 30 days prior to the first administration of IP
- 16. History of alcohol abuse or excessive intake of alcohol as judged by the investigator
- 17. Positive screen for drugs of abuse or alcohol at the pre-entry visit or on admission to the study unit
- 18. History of severe allergy/hypersensitivity or ongoing allergy/hypersensitivity, as judged by the investigator or history of hypersensitivity to IPs
- 19. Excessive intake of caffeine-containing drinks eg, coffee, tea, caffeine containing energy drinks and cola (more than 5 cups of coffee or equivalent per day)
- 20. Use of drugs with enzyme-inducing properties such as St John's Wort within 3 weeks before the first administration of IP
- Use of any prescribed or non-prescribed (over-the-counter (OTC)) medication including aspirin, NSAIDs such as ibuprofen, or any other drug known to increase the propensity for bleeding or need for antacids, or analgesics (other than paracetamol/acetaminophen), nasal anticongestants, herbal remedies, vitamins and minerals during the 2 weeks prior to the first administration of the IP or longer if the medication has a long half-life. Occasional use of paracetamol/acetaminophen is allowed for minor pains and headache.
- 22. Any intake of grapefruit, grapefruit juice, cranberry juice, Seville oranges, Seville orange marmalade or other products containing grapefruit, cranberry or Seville oranges within 14 days before the first administration of IP

- 23. Plasma donation within 1 month of the pre-entry visit or any blood donation/blood loss >500 mL during the 3 months prior to the pre-entry visit
- 24. Judgement by the investigator that the healthy volunteer should not participate in the study if they are considered unlikely to comply with study procedures, restrictions and requirements
- 25. Platelet count $<150 \times 10^9/L$ on Day -1 or any other conditions that would increase the risk of bleeding
- 26. Previous bone marrow transplant (applies to the requirement for CYP2C19 genotyping)
- Whole blood transfusion within 120 days of the date of genetic sample collection (applies to the requirement for CYP2C19 genotyping)

Procedures for withdrawal of incorrectly enrolled healthy volunteers see Section 5.3.

